## 7. Study endpoint/completion criteria

- a. Patient Completion of Study: If a study patient has completed the final visit (Visit 5) of the study, he/she is considered to have completed the study.
- b. Patient Discontinuation/Withdrawal: Each study patient may voluntarily discontinue the study at any time they choose. Study patients who cannot complete the study for administrative reasons (e.g., non-compliance, failure to meet visit schedule, etc.) will be discontinued from the study. Study patients discontinued during the enrollment phase (prior to surgery) of the study will be replaced.
- c. Patient Termination: A study patient will be terminated if the study patient develops any severe adverse event that may be related to the study. A study patient will receive appropriate treatment at the discretion of the investigator. Notification of termination will be clearly documented. These study patients are considered to have completed the study and will not be replaced.
- d. Study Termination: The investigator with appropriate notification may terminate the study. If, after clinical observations, the investigator feels that it may be unwise to continue the study, he may stop the study.
- e. Study Completion: The study will be complete when all enrolled patients have completed Visit 5 or have been terminated from the study.

## ADVERSE EVENTS AND DEVIATION REPORTING

All efforts will be made to look for possible adverse events or untoward findings. If an adverse event occurs, the safety and welfare of the subject will be the priority. Appropriate medical intervention will be made. Ocular adverse events observed by the investigator or reported by the subject, and in the investigator's opinion to be directly related to any of the devices being evaluated, will be recorded on an Adverse Event Case Report Form. Resolution of the adverse event will be recorded on the Adverse Event Follow-Up Form.

This is an Investigator Initiated Trial; however, notification of a serious ocular adverse event directly related to the evaluated devices will be made to the device manufacturer within 24 hours. Carolina Eyecare Physicians will support the manufacturer in the following-up of all events so that complete information is available to maintain patient safety and for them to comply with the appropriate regulatory reporting requirements.

Adverse events and deviations will be reported to the IRB following the IRB's Reporting Guidelines for Unanticipated Problems, Deviations, and Other Safety Information.

#### **SAMPLE SIZE**

Sample size calculations are based on a presumed t-test of refractive cylinder and corneal astigmatism between the two study groups. An alpha of 0.05 and a power of 0.8 were used. The standard deviations of the variables above have been previously estimated at about 0.35D. A difference of 0.25D would be clinically relevant. Using the information above, to reliably detect a difference between groups would require 34 eyes in each group. Spherical equivalent refraction, corneal astigmatism and refractive cylinder are likely to be highly correlated. Allowing for multiplicity of results, approximately 10% more eyes are required per additional correlated endpoint. In this case, 20% more eyes would be required, for a total of 40 eyes (20 subjects) per group.

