### **STUDY DESIGN AND METHODS:**

1. **Test article:** The VERION™ Image Guided System: Digital Surgical Planning and Positioning Tools + ORA System with VerifEye or VerifEye +.
2. **Study Design:** Prospective, randomized, contralateral eye study.
3. **Subjects:**
  - a. **Inclusion Criteria:**  
Subjects MUST fulfill the following conditions to qualify for enrollment into the trial
    1. Subject is undergoing bilateral cataract extraction or refractive lens exchange with intraocular lens implantation and astigmatism correction.
    2. Gender: Males and Females.
    3. Age: 50 years and older.
    4. Willing and able to provide written informed consent for participation in the study
    5. Willing and able to comply with scheduled visits and other study procedures.

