**b. Measurements and evaluations**

1. Visit 1: Informed consent process will be conducted at this visit. Assessments include uncorrected and best-corrected ETDRS visual acuity (UCVA / BCVA), manifest refraction, intraocular pressure (IOP), and slit lamp examination including dilated fundus exam, auto refractor keratometry, Lenstar, VERION™ Reference Unit, and corneal topography (Atlas). Both IOL power and astigmatism correction will be calculated using the surgeon's current standard of care as well as using the VERION™ Image Guided System: Digital Surgical Planning. Any testing that is part of the site's standard of care preoperative cataract surgery evaluation may be performed prior to the informed consent being signed provided these tests are conducted within 90 days of the surgery and notation of the date performed is entered onto the source document.

The first eye undergoing surgery will be randomized to either one of the two groups: Group A (surgeon standard of care) or B (VERION™ Image Guided System + ORA System with VerifEye or VerifEye +). The fellow eye will be assigned to the alternate group. Eyes will be randomized after all calculations have been completed. Prior to randomization, all measurements, IOL power and astigmatism correction calculations will be reviewed following the practice standard of care to determine subject's eligibility for astigmatism correction with toric lens or corneal incisions. If it is determined that the measurements are not consistent then subject will be excluded from the study.

The surgeon's standard pre cataract surgery treatment will be used in all his patients.

2. Visit 2: The surgeon may use his preferred cataract extraction technique (manual or laser) for eyes randomized to Group A. Eyes randomized to Group B will undergo laser assisted phacoemulsification (primary incision, capsulorhexis and lens fragmentation) using the surgeon's preferred laser settings. The secondary incision will be made with the laser or manually, at the surgeon's discretion. The lens will be implanted in the bag. The surgeon's standard post cataract surgery treatment will be used in all his patients.
3. Visit 3: Assessment will include uncorrected ETDRS visual acuity, intraocular pressure, slit lamp examination, corneal incision location and/or toric IOL orientation.

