#### **STATISTICAL CONSIDERATIONS**

All data will be collected by the research team. Data will be entered into a database. The database will be password protected and access will be restricted to study personnel. Data analysis will be performed without patient identification. Statistical analysis will be done using standard descriptive statistics and other tests as deemed appropriate based on the characteristics of the data to be analyzed. Secondary endpoints will be analyzed only if the primary endpoint demonstrates a statistically significant difference between groups. Corneal and refractive astigmatism are likely to be correlated. A Bonferroni correction will be applied where indicated for evaluating significance. Mean spherical equivalent refraction is not expected to be highly correlated to the measured astigmatism, nor is mean keratometry, so multiplicity considerations will not be required for these variables. All statistical tests will be two-sided and interpreted at a 5% significance level. Comparisons between the two groups will be made. Data analysis will be conducted by a third party consultant.

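### The sample size section ignores the pairing of eyes: with no between-eye correlation or SD of the difference given, 34 is only a conservative bound and 0.8 is not the power of this design

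*Combined protocol and SAP*

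**What the plan says.** The design is paired within subject. STUDY DESIGN AND METHODS, item 2, calls it a "Prospective, randomized, contralateral eye study". Section 6.b, Visit 1, says "The first eye undergoing surgery will be randomized to either one of the two groups" and then "The fellow eye will be assigned to the alternate group". Every subject therefore contributes one eye to Group A and one to Group B.

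The SAMPLE SIZE section sets out its calculation as follows:

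- Test: "Sample size calculations are based on a presumed t-test of refractive cylinder and corneal astigmatism between the two study groups".
- Error rates: "An alpha of 0.05 and a power of 0.8 were used". STATISTICAL CONSIDERATIONS adds "All statistical tests will be two-sided and interpreted at a 5% significance level".
- Variability: "The standard deviations of the variables above have been previously estimated at about 0.35D".
- Target difference: 0.25 D.
- Result before the multiplicity allowance: "would require 34 eyes in each group".

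A 20% allowance for multiplicity brings the figure to 40 eyes per group, which the section equates with 20 subjects. The only correlations mentioned there or in STATISTICAL CONSIDERATIONS are between endpoints. None is between the two eyes of a subject.

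**The concern.** In a contralateral-eye trial, the precision of the treatment comparison depends on the SD of the within-subject difference, 0.35 × √(2(1 − r)). It does not depend on the per-eye SD alone. The section supplies the 0.35 D but neither r nor the SD of the difference, and it counts eyes per group rather than subjects. Its inputs therefore do not determine the power of the comparison that the trial will make.

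What is at stake is whether the planned number of subjects can be judged adequate. At 34 to 40 subjects the missing parameter decides only how far power exceeds the target. At 20 subjects it decides whether the target is met at all.

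**Working it through.** **Inputs.** Difference 0.25 D, per-eye SD 0.35 D, alpha 0.05 and power 0.80 come from SAMPLE SIZE. Two-sided testing comes from STATISTICAL CONSIDERATIONS. The documents give no r, so the values of r below are assumptions shown as a range.

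**Step 1: reproduce the plan's 34.** For two independent groups of n eyes, the noncentrality is 0.25 / (0.35 × √(2/n)) with 2n − 2 degrees of freedom.

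- n = 31 gives power 0.790, n = 32 gives 0.803 and n = 34 gives 0.827. The requirement is 32 per group.
- The normal approximation gives 2 × (0.35 × (1.960 + 0.842) / 0.25)² = 30.8, so 31.

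**Step 2: try the paired readings.** For n pairs, the noncentrality is 0.25 × √n / SD_diff with n − 1 degrees of freedom.

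- If 0.35 D were the SD of the difference, 18 pairs would suffice (0.790 at 17, 0.815 at 18). That is far from 34, so the section is not using 0.35 D in that way.
- If 0.35 D is the per-eye SD and r = 0, SD_diff = 0.35 × √2 = 0.495 D and 33 pairs are needed.

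The stated 34 lies within two of the independent-eyes answer (32) and within one of the paired answer at r = 0 (33). These two are the same variance assumption with different degrees of freedom. In either case no between-eye correlation has entered the calculation.

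**Step 3: the paired design over a range of r.** SD_diff = 0.35 × √(2(1 − r)).

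| Assumed r | SD_diff (D) | Pairs for 80% power | Power, 20 pairs | Power, 34 pairs | Power, 40 pairs |
|---|---|---|---|---|---|
| 0 | 0.495 | 33 | 0.573 | 0.816 | 0.876 |
| 0.3 | 0.414 | 24 | 0.726 | 0.927 | 0.961 |
| 0.5 | 0.350 | 18 | 0.858 | 0.981 | 0.993 |
| 0.7 | 0.271 | 12 | 0.974 | 0.999 | >0.999 |

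Worked example at r = 0 and 34 pairs: noncentrality 0.25 × √34 / 0.495 = 2.945 on 33 degrees of freedom, power 0.816.

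**Step 4: thresholds in r.** With 34 pairs, power is 0.80 or more for any r above about −0.04. With 20 pairs, power reaches 0.80 only at r of about 0.42 or more.

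**The case against.** The strongest reply is that the omission is on the safe side. At r = 0, the least favourable value in the range, 34 pairs already give 0.816, and any positive r adds to that. The conservative paired requirement is 33, so the correction to the headline number is from 34 to 33. This stands, and it limits how much weight the point can carry.

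Three stronger readings are tempting, and the documents do not support them.

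- *The section states an unpaired calculation.* It does not say unpaired or independent. That is inferred from the between-group wording, the per-eye SD and the absence of r. The arithmetic cannot separate 32 per group from 33 pairs at r = 0. What is established is that no between-eye correlation was used.
- *The number 34 is invalid or the trial is underpowered.* At 34 or 40 pairs no value in the table falls below 0.816. Every power below 0.80 is at 20 pairs. It arises only if the closing reference to 20 subjects means 20 in total, and that count mismatch is a separate defect whose effect should not be charged twice.
- *The primary analysis will be unpaired.* STATISTICAL CONSIDERATIONS leaves the tests open according to the nature of the data, so a paired analysis remains available. It names no paired method, however, so it does not supply the missing parameter either.

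The reply does not dispose of the point. The safe direction is assured only at 34 to 40 subjects. Correcting the subject count would settle how many pairs are meant, but it would not give the power of that number.

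**Conclusion.** The point holds in a limited form. The sizing takes no account of the pairing, so the stated 34 is a conservative upper bound on the number of pairs for any r of zero or above, and the stated 0.8 does not describe the paired design. The power of that design is 0.82 to 0.98 at 34 pairs and 0.88 to 0.99 at 40 pairs, for r from 0 to 0.5. If 20 subjects in total are meant, it is 0.57 to 0.86 over the same range, and adequacy rests on an r of about 0.42 or more that the plan never states.

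These figures assume the plan's 0.25 D and 0.35 D, the same SD in both groups, a two-sided paired t-test at 0.05 with no multiplicity adjustment, complete pairs, and r not negative. The values of r are illustrative. This is a gap in the justification of the sample size. It is not evidence that a trial of 34 to 40 subjects would be too small.

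**What to change.** Restate the SAMPLE SIZE section as a paired t-test, counted in subjects (pairs). Give either the assumed SD of the within-subject difference, or the per-eye 0.35 D with an assumed r and its basis. State the resulting power at the number of subjects actually planned for r = 0, 0.3 and 0.5. If no estimate of r is available, take r = 0 (33 pairs before the multiplicity allowance) as the conservative default.

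The cost is a few lines of recalculation and protocol wording. No change in enrolment is asked for, and no patient procedure is affected. The one drawback is that a single stated power becomes a range.

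### The stated 40 eyes (20 subjects) per group cannot occur in a contralateral-eye design: 40 eyes per group needs 40 subjects, and 20 subjects give 20 eyes per group, fewer than the plan's own 34

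*Combined protocol and SAP*

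**What the plan says.** Under Study Design and Methods, the trial is a "Prospective, randomized, contralateral eye study", and the first inclusion criterion limits entry to patients having surgery on both eyes. The Visit 1 text under Measurements and evaluations sets the allocation: "The first eye undergoing surgery will be randomized to either one of the two groups", and then "The fellow eye will be assigned to the alternate group".

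The Sample Size section starts from a two-group comparison: "Sample size calculations are based on a presumed t-test of refractive cylinder and corneal astigmatism between the two study groups". With alpha 0.05, power 0.8, an SD of about 0.35 D and a difference of 0.25 D, it states that "to reliably detect a difference between groups would require 34 eyes in each group". It then adds 10% for each of two further correlated endpoints and ends: "In this case, 20% more eyes would be required, for a total of 40 eyes (20 subjects) per group".

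The text reviewed gives no other number of subjects. The completion rule in section 7 refers only to whoever has been enrolled: "The study will be complete when all enrolled patients have completed Visit 5 or have been terminated from the study".

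**The concern.** The closing parenthesis puts both eyes of a subject in the same group. The allocation rule forbids that, because no subject belongs to a single group. Forty eyes from 20 subjects makes sense as a count for the whole study, and 40 eyes per group makes sense as the result of the calculation. The sentence joins the two, and they differ by a factor of two.

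This is the figure that sets enrolment. Anyone who takes 20 as the number of subjects would run the trial with half the eyes per group that the calculation asks for. The loss would fall on the primary endpoint, refractive cylinder at 3 months. It would also reach the secondary endpoints, because Statistical Considerations allows them to be analysed only if the primary result is significant.

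**Working it through.** **Inputs.** From Sample Size: SD 0.35 D, difference 0.25 D, alpha 0.05, power 0.8, 34 eyes per group, 20% inflation. From Statistical Considerations: two-sided tests. From the allocation rule: one eye per subject in each group. The documents give no between-eye correlation, so the values of ρ below are assumptions.

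**1. Reproducing the plan's eye counts.**
- Standardised difference: 0.25 / 0.35 = 0.714.
- Normal approximation: n = 2 × [0.35 × (1.960 + 0.842) / 0.25]² = 30.8, so 31 per group. The exact two-sample t-test needs 32. The plan's 34 is close to this and slightly generous, so it was evidently built on independent groups. A one-sided test would need only 25.
- Inflation: 34 × 1.2 = 40.8, against the stated 40. The 40 is therefore a per-group number and not a total over both groups.

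**2. Converting eyes to subjects.** With one eye per subject in each group, eyes per group = subjects.

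| Subjects | Eyes per group | Eyes in all | Against 34 per group |
|---|---|---|---|
| 20 | 20 | 40 | 14 short |
| 34 | 34 | 68 | met |
| 40 | 40 | 80 | 6 over |

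No row has 40 eyes per group from 20 subjects.

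**3. Power under the plan's two-sample t-test.** The noncentrality is 0.25 / [0.35 × √(2/n)] on 2n − 2 degrees of freedom.

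| Eyes per group | Power for 0.25 D | Difference detectable at 0.80 power |
|---|---|---|
| 20 | 0.595 | 0.318 D |
| 34 | 0.827 | 0.241 D |
| 40 | 0.884 | 0.222 D |

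At 20 per group the detectable difference exceeds the 0.25 D that the plan regards as clinically relevant. If the true difference is 0.25 D, the chance that the primary test fails, and so blocks the secondary analyses, is 1 − 0.595 = 0.405 at 20 per group and 1 − 0.884 = 0.116 at 40.

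**4. Power if the eyes are analysed as pairs.** The SD of the within-subject difference is 0.35 × √[2(1 − ρ)].

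| Assumed ρ | SD of difference | Power, 20 subjects | Power, 40 subjects | Subjects for 0.80 |
|---|---|---|---|---|
| 0 | 0.495 D | 0.573 | 0.876 | 33 |
| 0.25 | 0.429 D | 0.697 | 0.949 | 26 |
| 0.5 | 0.350 D | 0.858 | 0.993 | 18 |

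Twenty subjects reach 0.80 at ρ of about 0.415, where the SD of the difference is about 0.379 D. Forty subjects exceed 0.80 at every value shown.

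**The case against.** The strongest reply is that the parenthesis reads 20 subjects per group. Taken literally over two groups, that makes 40 subjects and 80 eyes, and the allocation rule then yields the 40 eyes per group that the calculation needs. On that reading the total is adequate and only the label is wrong. This stands in part: the shortfall arises only if 20 is taken as the study total. But the text never states 40 subjects, and counting subjects per group is wrong for this design on either reading.

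A second reply is that pairing could rescue 20 subjects, since the plan speaks only of a t-test and leaves the choice of tests open. That is also fair. Power with 20 subjects runs from 0.57 to 0.86 over assumed correlations of 0 to 0.5, so inadequate power is neither shown nor excluded. The plan states no paired test and no correlation, so it cannot support 20 subjects as it stands. Nor is 0.88 a target of the plan: the target is 0.8, and the extra 20% is there for multiplicity.

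Third, the opening pages were not available to this review and may state a total. That would show which number was meant, but it would not make the Sample Size sentence correct.

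Three further points are true but separate. Strictly, 40.8 rounds up to 41, which moves two-sample power only from 0.88 to 0.89. Subjects can be lost through the intraoperative exclusions and are not always replaced. And the Sample Size and Statistical Considerations sections disagree on whether spherical equivalent is highly correlated with astigmatism.

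**Conclusion.** The concern holds, and the sentence must be corrected. The contradiction follows from the allocation rule and the Sample Size sentence alone and needs no outside assumption. The enrolment target is ambiguous by a factor of two, 20 or 40 subjects.

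If 20 is the study total, each group has 20 eyes against the 34 required, and power under the plan's own two-sample calculation is 0.60. With a paired test, the adequacy of 20 subjects depends on an unstated between-eye correlation of about 0.42 or more. If 40 is the study total, the trial has power of at least 0.88 on either basis at zero or positive correlation, and only the wording is wrong. The plan's own arithmetic (34 × 1.2) favours 40. The finding is that the enrolment number contradicts the design; it does not establish that the trial is underpowered.

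**What to change.** Replace the last sentence of Sample Size with one consistent statement, in one of two forms:

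- **40 subjects (80 eyes), one eye of each subject in each group.** The 34 × 1.2 step supports this, and the power calculation need not be redone. Moving it to a paired basis is optional, because ignoring a positive between-eye correlation is conservative.
- **20 subjects (40 eyes), 20 eyes in each group.** In this case restate power for a paired t-test, giving the assumed between-eye correlation or SD of within-subject differences and its source.

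Either way, drop the count of subjects per group, and say whether the number is enrolled subjects or subjects evaluable at 3 months.

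The cost is one corrected paragraph. If the team has been working to 20 subjects, it must either double enrolment to reach 40 eyes per group, or keep 20 and report the power that number supports: 0.60 on the plan's two-sample basis, or a paired figure that depends on the correlation it can justify.

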#### **STATISTICAL CONSIDERATIONS**

All data will be collected by the research team. Data will be entered into a database. The database will be password protected and access will be restricted to study personnel. Data analysis will be performed without patient identification. Statistical analysis will be done using standard descriptive statistics and other tests as deemed appropriate based on the characteristics of the data to be analyzed. Secondary endpoints will be analyzed only if the primary endpoint demonstrates a statistically significant difference between groups. Corneal and refractive astigmatism are likely to be correlated. A Bonferroni correction will be applied where indicated for evaluating significance. Mean spherical equivalent refraction is not expected to be highly correlated to the measured astigmatism, nor is mean keratometry, so multiplicity considerations will not be required for these variables. All statistical tests will be two-sided and interpreted at a 5% significance level. Comparisons between the two groups will be made. Data analysis will be conducted by a third party consultant.

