## 6. Study Visit Schedule and Assessments (Table 1).

- a. **Visit Schedule:** Patients will be examined at the following intervals:

1. Visit 1: Screening and enrollment: Preoperative evaluation completed not more than eight weeks before surgery

2. Visit 2: Day of Surgery
3. Visit 3: Day 1 (12 to 48 hrs) after surgery
3. Visit 4: Month 1:  $30 \pm 10$  days postoperative after second eye surgery
4. Visit 5: Month 3:  $90 \pm 15$  days postoperative after second eye surgery

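### The primary analysis is left open: no within-subject comparison adjusted for each eye's preoperative corneal astigmatism is prespecified, although the design and Visit 1 data allow one

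*Combined protocol and SAP*

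**What the plan says.** The Sample Size section rests on a "presumed t-test of refractive cylinder and corneal astigmatism between the two study groups". It assumes an SD of about 0.35 D, a difference of 0.25 D, alpha 0.05 and power 0.8.

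The Statistical Considerations section names no primary test. It offers descriptive statistics and "other tests as deemed appropriate based on the characteristics of the data to be analyzed", then adds: "All statistical tests will be two-sided and interpreted at a 5% significance level". It mentions no subject effect, pairing, covariate or eye-order term. It makes every secondary analysis conditional on a significant primary result.

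The design is contralateral. The first eye is randomized and the fellow eye receives the other treatment. Section 6.b and Table 1 place autorefractor keratometry, Lenstar, VERION Reference Unit and Atlas topography at Visit 1. Also before randomization, the plans are reviewed for "eligibility for astigmatism correction with toric lens or corneal incisions". The Month 1 and Month 3 visits are both timed as "days postoperative after second eye surgery".

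**The concern.** Randomizing within subject balances everything the two eyes share. It does not balance what differs between them. Preoperative corneal astigmatism is an eye-level quantity. The inclusion criteria set no astigmatism range and do not require the two eyes to be similar. A between-eye difference in starting astigmatism may carry through to residual cylinder and add noise to the paired difference. In a small trial it may also favour one group by chance.

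An open method has a second cost. Pairing and covariates could be chosen after the results are known, and the primary p-value decides whether any secondary endpoint is analysed.

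**Working it through.** **Inputs from the Sample Size section:** difference 0.25 D, SD 0.35 D, alpha 0.05 (two-sided per Statistical Considerations), power 0.80.

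**Inputs assumed, because the documents give none:** within-pair correlation rho of residual cylinder, and r, the correlation between the between-eye difference in preoperative astigmatism and the between-eye difference in residual cylinder.

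**1. The plan's own figure.** By the normal approximation, n per group = 2 × (1.960 + 0.842)² × 0.35² / 0.25² = 2 × 7.85 × 1.96 = 30.8, so 31. The exact two-sample t-test needs 32 (power 0.803). The stated 34 gives power 0.827, so it is reproduced within two eyes. The 20% increase gives 34 × 1.2 = 40.8, stated as 40 eyes per group and equated with 20 subjects. In a contralateral design 20 subjects give 20 pairs and 40 eyes per group need 40 subjects, so both readings are shown.

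**2. Pairing.** SD of the paired difference = 0.35 × √(2(1 − rho)).

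| rho | SD of difference | Pairs for 80% power | Power, 20 pairs | Power, 40 pairs |
|---|---|---|---|---|
| 0 | 0.495 | 33 | 0.573 | 0.876 |
| 0.3 | 0.414 | 24 | 0.726 | 0.961 |
| 0.5 | 0.350 | 18 | 0.858 | 0.993 |

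If the pairs were analysed as independent samples at rho = 0.3 with 20 per group, the standard error used would be 0.35 × √(2/20) = 0.111 D, against 0.414/√20 = 0.093 D for the paired analysis.

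**3. Adjusting for preoperative astigmatism, ignoring estimation cost.** Residual variance is multiplied by 1 − r², which is 0.91 at r = 0.3 and 0.75 at r = 0.5. At rho = 0.3, power with 20 pairs becomes 0.766 and 0.841. With 40 pairs it becomes 0.974 and 0.990.

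**4. The same, with the coefficients estimated.** Simulation of the paired difference: 20 pairs, rho = 0.3. The last column also assumes that correction type differs between eyes in 30% of subjects and that order and type have no effect.

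| r | Unadjusted | Astigmatism only | Astigmatism + order + type |
|---|---|---|---|
| 0 | 0.73 | 0.70 | 0.65 |
| 0.3 | 0.73 | 0.74 | 0.69 |
| 0.5 | 0.73 | 0.81 | 0.77 |

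The single covariate loses about 0.03 at r = 0 and gains about 0.08 at r = 0.5. Under these assumptions, adding order and type costs a further 0.04 to 0.05 at every r. An eye-level mixed model may recover part of that cost; this was not simulated.

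**5. Eye order.** With 20 subjects and simple randomization, a split of first eyes of 13:7 or worse has probability 2 × 0.132 = 0.263. If order had a 0.10 D effect (assumed), a 13:7 split would move the group difference by 0.10 × (13 − 7)/20 = 0.03 D. That is about a third of the 0.093 D standard error and 12% of the 0.25 D target.

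**The case against.** A reader might infer that the plan commits to an unadjusted t-test. It does not: the t-test is a sizing presumption, and the analysis section leaves the method open. A suitable model could still be chosen, so the defect is the missing prespecification.

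A reader might also infer bias. Randomization keeps the unadjusted comparison unbiased, and the subject-level factors are balanced by design.

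The gain may be small or absent. Treatment is calculated from each eye's own keratometry, so residual cylinder may be nearly unrelated to starting astigmatism. In that case adjustment costs a little power. On the 40-pair reading there is little left to gain. All of this stands.

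It is tempting to put baseline astigmatism, correction type and eye order all into the primary model. With 20 pairs that can lower power below the unadjusted test (0.69 against 0.73 at r = 0.3), unless order or type truly matters.

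It is also tempting to say that the first eye is always measured later than its nominal time because visits run from second-eye surgery. The Month 3 window is 90 ± 15 days. With an illustrative 7-day gap between eyes and a visit at day 75, the first eye is seen at day 82, before its nominal time. The gap between eyes is not stated. The rule that the preoperative visit falls within eight weeks of surgery may bound it, if applied to each eye.

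**Conclusion.** The point holds as a gap in prespecification with a modest precision benefit. The plan fixes neither a within-subject analysis nor adjustment for a covariate that it already collects on each eye.

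Pairing is the larger part: as rho goes from 0 to 0.5, the pairs needed for 80% power fall from 33 to 18. Adjustment for astigmatism changes power with 20 pairs at rho = 0.3 by about −0.03 to +0.08 across r = 0 to 0.5, and changes little with 40 pairs. These sizes rest on assumed correlations and on the plan's SD of 0.35 D. The documents do not allow a single figure. The other benefits, protection from chance imbalance between fellow eyes and a method fixed before the data are seen, do not depend on r being large.

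**What to change.** In Statistical Considerations, state the primary analysis as a linear mixed model for 3-month residual refractive cylinder. It should have a random subject effect, a fixed group effect and that eye's Visit 1 corneal astigmatism as covariate. Report the adjusted group difference with its 95% CI.

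Name one keratometry source in advance and use it for both groups. Visit 1 has several, and the agreement of Lenstar with Verion readings is itself a secondary endpoint.

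As a sensitivity analysis, add eye order and planned correction type. Define correction type for both eyes from the standard-of-care plan made before randomization. Two plans exist for each eye, and using the plan actually followed could make the covariate depend on treatment. List the categories, including any combined toric and incision plan.

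The cost is wording only, with no new assessment. Eye order is known from the randomization but has no line of its own in Table 1, so record it explicitly. The statistical cost is one degree of freedom and a small loss of power if r is near zero.
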